10.14 Derivations for Exposure Variables

The following variables will be derived for SOT101 and pembrolizumab respectively.

Variable	Definition for SOT101	Definition for pembrolizumab	Definition for combination therapy
Duration of exposure (days)	Last dose date – Start dose date +1	Last dose date – Start dose date +1	Last dose date of either SOT101 or Pembrolizumab, whichever is later – Start dose date of SOT101 or

			pembrolizumab, whichever is earlier +1
Cycle started	A patient is considered to have started a cycle if they received at least one dose of SOT101 in that cycle, per the Study Exposure CRF page.	A patient is considered to have started a cycle if they received at least one dose of pembrolizumab in that cycle, per the Study Exposure CRF page.	A patient is considered to have started a cycle if they received at least one dose of SOT101 and pembrolizumab in that cycle, per the Study Exposure CRF page.
Completed Cycle	A cycle is considered completed if the patient received 4 doses of SOT101 and 1 dose of pembrolizumab in that cycle, or the patient started the next cycle and received at least one dose of SOT101 in that cycle.	A cycle is considered completed if the patient received 4 doses of SOT101 and 1 dose of pembrolizumab in that cycle, or the patient started the next cycle and received pembrolizumab in that cycle.	
Duration of cycle (days)	The day prior to the date of cycle start (day 1 in each cycle) will be considered as the end of the previous cycle. For the last cycle, 21 days will be used.		
Planned cumulative dose (applicable unit)	$(12 \text{ (\mu g/kg/dose)} * 4 \text{ doses}) * \text{Number of cycles started (\mu g/kg)}$	200 mg * Number of cycles started (mg)	
Real dose administered (applicable unit)	$(2 \times \text{Total volume administered}) / \text{patient weight (\mu g/kg)}$	As per CRF (mg)	
Actual cumulative dose (all cycles)	Sum of the real doses ($\mu \text{g/kg}$) administered	Sum of the real doses (mg) administered	
Actual cumulative dose for completed cycles* (Not presented, required for calculation of ADI)	Sum of the real doses ($\mu \text{g/kg}$) administered considering only completed cycles	Sum of the real doses (mg) administered considering only completed cycles	
Duration of exposure (days) for completed cycles *	Considering only completed cycles: End date of last completed cycle – Start dose date of SOT101 or Pembrolizumab, whichever is earlier + 1		

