Intended dose Intensity	$12 \text{ (\mu g/kg/dose)} * 4 \text{ doses/ 21 day (\mu g/kg /day)}$	200 mg/ 21 day (mg/day)	
Actual dose intensity (ADI) ($\mu \text{g/kg /day}$) or (mg/day) *	Considering only completed cycles; Actual cumulative dose/ Duration of exposure (days)		
Actual dose intensity by cycle ($\mu \text{g/kg /day}$) or (mg/day) *	Considering only completed cycles: Actual cumulative dose in that cycle / Duration of cycle (days)		
Relative dose intensity by cycle (%)	Considering only completed cycles:		

	100 * (Actual dose Intensity for that cycle/Intended dose intensity for that cycle)	
Overall Relative dose intensity (%) *	Considering only completed cycles: 100 * (Actual dose Intensity /Intended dose)	
Compliance with planned dose (%)	100 * (Actual cumulative dose / Planned cumulative dose at that cycle, taking into account per protocol dose reductions)	

* Only completed cycles as defined should be considered for derivation

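### SAP 10.14: the overall relative dose intensity formula has the wrong denominator, and the completed-cycle rule drops a partly dosed final cycle from the summary

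*SAP*

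**What the plan says.** The exposure table in SAP 10.14 builds RDI in four steps.

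- **Which cycles count.** Actual dose intensity, RDI by cycle and overall RDI are all limited to completed cycles, and the table footnote repeats this: "Only completed cycles as defined should be considered for derivation".
- **What completed means.** SOT101 has two routes. The first is full dosing: "A cycle is considered completed if the patient received 4 doses of SOT101 and 1 dose of pembrolizumab in that cycle". Under the second, a cycle with missed doses still qualifies once SOT101 has been given again in the cycle that follows. The pembrolizumab column has the same first route. Its second route needs pembrolizumab in the next cycle.
- **How long a cycle lasts.** A cycle ends the day before the next one starts. For the final one: "For the last cycle, 21 days will be used".
- **The ratio.** A row named "Intended dose Intensity" is defined as 12 µg/kg × 4 doses / 21 days for SOT101 and as "200 mg/ 21 day (mg/day") for pembrolizumab. The by-cycle row uses it: "100 * (Actual dose Intensity for that cycle/Intended dose intensity for that cycle"). The overall row does not: "100 * (Actual dose Intensity /Intended dose").

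SAP 12.5.1 summarizes exposure duration, cycles started, number of doses, cumulative dose, actual dose intensity and RDI on the ASaT, efficacy and per protocol populations, and plots RDI by cycle. Compliance, which is based on cycles started and allows for per-protocol dose reductions, is only listed.

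**The concern.** The overall row divides a rate per day by something called a dose. That is dimensionally wrong, and the named denominator does not exist as a variable. A table of derivations is a programming specification, so it should not leave the programmer to guess.

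The completed-cycle rule is a different matter. A cycle in which SOT101 stops after one to three injections satisfies neither route to completion, so it vanishes from RDI. That cycle is often where a tolerability problem appears, although the rule applies equally to stops for progression, withdrawal or death. Such cycles are foreseeable: SOT101 is given on four days per cycle, and protocol Table 6.2 provides for withholding and permanent discontinuation.

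At stake is how the exposure section reads. A summarized and plotted RDI can show 100% for a patient who did not receive the planned doses of the last cycle. The only patient-level ratio that counts all started cycles is left to a listing.

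**Working it through.** The SAP states no numerical RDI, so there is no figure to reproduce. The check applies its formulas to example dosing patterns.

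**Inputs (SAP 10.14).** SOT101 12 µg/kg per dose, four doses per cycle, pembrolizumab 200 mg per cycle, 21 days for the last cycle. Assumed: every cycle lasts 21 days without delay, every SOT101 dose is 12 µg/kg, and pembrolizumab is given on day 1 of each started cycle.

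**Denominator.**

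- Intended dose intensity, SOT101: 48/21 = 2.286 µg/kg/day. Pembrolizumab: 200/21 = 9.524 mg/day.
- Full dosing over the defined denominator: 100 × 2.286/2.286 = 100%.
- Full dosing read literally, if the intended dose means 48 µg/kg per cycle: 100 × 2.286/48 = 4.76%. If it means 12 µg/kg per dose: 100 × 2.286/12 = 19.05%. Pembrolizumab over 200 mg: 100 × 9.524/200 = 4.76%. These carry units of 1/day and are not percentages of anything.

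**Completed-cycle rule (SOT101, correct denominator).**

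- SAP version: 100 × (dose in completed cycles / days in completed cycles) / 2.286.
- Started-cycle version: the same, over all started cycles, with the last taken as 21 days.

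| SOT101 doses per cycle | SAP RDI | RDI over started cycles |
|---|---|---|
| 1, 2 or 3 in cycle 1, then stop | no value | 25%, 50% or 75% |
| 4, then 1 | 100% | 60/96 = 62.5% |
| 4, then 2 | 100% | 72/96 = 75% |
| 4, then 3 | 100% | 84/96 = 87.5% |
| 4, 4, then 1 | 100% | 108/144 = 75% |
| 4, 4, 4, then 1 | 100% | 156/192 = 81.25% |
| five full cycles, then 1 | 100% | 252/288 = 87.5% |
| 3, then 1 | 75% | 48/96 = 50% |
| 2, 2, then 1 | 50% | 60/144 = 41.7% |
| 2, then 3 | 50% | 60/96 = 62.5% |

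The last three rows set the limits of the point. Doses missed in a non-final cycle still count, because starting the next cycle makes that cycle complete. The final row shows that the distortion can run downward.

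**A group illustration with assumed patients.** Ten patients: five with four full cycles, two with 4, 4, 2, one with 4, 1, and two with two doses in cycle 1 only. The SAP mean is 100% on n = 8. The started-cycle mean is (5 × 100 + 2 × 83.3 + 62.5 + 2 × 50)/10 = 82.9% on n = 10. The mix is invented to show the mechanism and does not estimate this trial.

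**Two related consequences.** Protocol 7.1 lets pembrolizumab continue after nanrilkefusp alfa (SOT101) stops for reasons other than progression. A patient with one injection in cycle 3 who goes on with pembrolizumab alone still has cycle 3 excluded for SOT101. Also, because the first pembrolizumab route requires four SOT101 doses, a patient given the full pembrolizumab dose but fewer than four SOT101 doses in an only cycle has no pembrolizumab RDI.

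**The case against.** The strongest reply is that leaving out a truncated final cycle is a legitimate, explicitly stated choice. Protocol 7.1 lists progression and death among the reasons for stopping. Charging such a patient a full 21-day cycle would make disease progression look like poor dose delivery. The two versions answer different questions. This stands, and it is why both should be shown rather than one replaced.

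Second, these patients are not hidden. SAP 12.5.1 tabulates patients by number of injections from 1 upward, together with cycles started and cumulative dose. The completed-cycle cumulative dose is marked as not presented, so the one summarized covers all cycles. Actual over planned dose for started cycles can therefore be approximated at group level. SAP 12.8.1.1 tabulates adverse events leading to dose reduction and to temporary or permanent discontinuation, and SAP 12.1 gives reasons for stopping treatment. This also stands. What is missing is a summarized patient-level ratio over started cycles.

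Third, the denominator is almost certainly a labelling slip, since the correct variable is defined and used in the by-cycle row. Agreed. A reader might infer that the slip makes patients look fully dosed, or that outputs near 5% are to be expected. The documents support neither: read literally, the slip pushes the figure down, and the result depends on an invented meaning for an undefined term.

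**Conclusion.** Both faults are present in SAP 10.14, and they are independent. The overall formula is wrong as printed. The completed-cycle rule gives 100% where earlier cycles were full and on time but the last was cut short, against 62.5% to 87.5% over started cycles in the examples. It gives no value at all for a stop part-way through cycle 1. That missing value matters only in the ASaT summary, because the efficacy and per protocol populations already exclude those patients (SAP 9.5 and 9.6).

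Stronger readings are tempting but do not hold:

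- That the rule targets toxicity: it covers any reason for stopping.
- That it always flatters: upward is the usual direction, not the only one.
- That RDI is the main tolerability measure: the tolerability endpoints are adverse events, laboratory findings, vital signs and ECG, and SAP 12.5.1 does not rank RDI above the other exposure summaries.

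The examples assume 21-day cycles without delay and full 12 µg/kg doses. The documents give no frequency of mid-cycle stops, so no trial-level bias can be stated. Response rate, the futility rules and the sample size do not depend on RDI. Severity is minor: exposure reporting only.

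**What to change.** 1. In the overall row of SAP 10.14, print 100 × (actual dose intensity / intended dose intensity), matching the by-cycle row.
2. Add a summary of RDI over all started cycles, with 21 days for the last cycle as the SAP already provides, beside the completed-cycle version. Label each clearly.
3. Report the number of ASaT patients with no completed-cycle RDI, for each drug.

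The cost is a table edit and one more summary, from data already collected, and it can be done before database lock. RDI will look less favourable in most cases. Final cycles cut short by progression or death will also lower the started-cycle figure, so a footnote should say that it reflects stops for any reason.

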10.15 Safety Variables

10.15.1 Treatment-emergent AEs

All AEs will be recorded in the database but not all on-treatment events will be considered as treatment-emergent e.g. if they are an improvement of an existing condition. A treatment-emergent AE (TEAE) is defined as an AE that started or worsened after the start of study treatment.

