### 8.3.8.2 Documenting on eCRFs

The reported term should be a medical diagnosis or sign/symptom of the event according to the CTCAE, version 5.0 (whenever possible), not a procedure. Each symptom in a constellation of symptoms should be listed separately if the investigator has not set a diagnosis.

Fluctuations or re-occurrences of a condition, which are considered normal for the patient and are recorded on the patient's eCRF medical history, do not need to be reported as an AE. However, if the condition deteriorates during the trial, it needs to be captured as an AE.

If the same AE occurs repeatedly, it must be assessed and documented separately each time.

If possible, each AE should be evaluated to determine:

- Event term (according to the CTCAE, version 5.0, not as reported by the patient) or a description of the AE in medical terms
- Severity grade or intensity of the event as assessed by the investigator (1-5 according to the CTCAE, version 5.0)
- Its causal relationship to nanrilefusp alfa and/or pembrolizumab, as assessed by the investigator (suspected; not suspected)
- Other suspected cause(s) of the event (e.g., concurrent disease, concomitant medication)
- Event duration, including onset date and end date
- Action taken with nanrilefusp alfa and/or pembrolizumab due to the reported event
- Other action taken
- Event seriousness (non-serious or serious AE)
- Event outcome

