### **9.3.3 Secondary endpoints analysis**

#### **9.3.3.1 Safety endpoints**

- TEAEs

A TEAE is defined as an AE that started or worsened at or after the start of study treatment.

TEAEs will be summarized with counts and percentages. These will be provided for the incidence of, but not limited to: any TEAE, any serious TEAE, any grade 3-5 TEAE, any drug-related TEAE, any serious and drug-related TEAE, any grade 3-5 and drug-related TEAE, temporarily discontinued due to a TEAE, permanently discontinued due to a TEAE, death. TEAE incidence frequencies by system organ class (SOC) and preferred term (PT) will also be provided.

- AESIs

AESIs will be summarized with counts and percentages by SOC and PT.

- Safety laboratory findings, vital signs, and ECG

Safety laboratory findings, vital signs measurements, and ECG data will be summarized accordingly (if categorical or continuous data). Laboratory results will be summarized using SI units as appropriate.

Further details on analyses to be performed by indication and overall will be specified in the final SAP.

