10.0 Conventions and Derivations

10.1 Study Treatment

The study treatment defined is the combination of SOT101 12 µg/kg subcutaneously and 200 mg pembrolizumab IV infusion.

Patients will be treated with SOT101 12 µg/kg subcutaneously on day 1 (± 1 day for the cycle start), day 2, day 8, and day 9 in combination with pembrolizumab 200 mg IV on day 1 in 3-week cycles.

Pembrolizumab will be administered as an IV infusion via peripheral or central venous line starting within 30 minutes after the first dose (day 1) of SOT101 in each 3-week cycle.

Start of study treatment is defined as the date and time of first dose of either SOT101 or pembrolizumab, whichever occurs earliest. Per protocol this should be SOT101.

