10.16.1 Imputation of Missing Dates for AEs and Concomitant Medication and Procedures

For the purposes of assigning AEs and concomitant medications to study periods the following algorithm will be used for missing or partial dates (AE start/stop dates and concomitant medication start/stop dates):

The actual (non-imputed) value for date will be presented in all data listings and imputed dates will only be used for programming purposes, such as TEAE derivation.

Start date

If the start date is completely missing (i.e., the day, month, and year are all unknown), the start date will be set to the date of the first dose of study medication

Missing day only

- If the month and year of the incomplete date are the same as the month and year of the **first dose date**, then the day of the **first dose date** will be assigned to the missing day.
- If either the year is before the year of the **first dose date** or if years are the same but the month is before the month of the **first dose date**, then the last day of the month will be assigned to the missing day.
- If either the year is after the year of the **first dose date** or if both years are the same but the month is after the month of the **first dose date**, then the first day of the month will be assigned to the missing day.

Missing month only

- The day will be treated as also missing and both month and day will be replaced according to the below procedure.

Missing day and month

- If the year of the incomplete date is the same as the year of the **first dose date**, then the day and month of the **first dose date** will be assigned to the missing fields.
- If the year of the incomplete date is not the same as the year of the **first dose date**, then January 1 will be assigned to the missing fields.

If the stop date is complete and the imputed start date is after the stop date, then the start date will be imputed using the stop date

Stop date

Missing day only

- If the month and year of the incomplete date are the same as the month and year of the **last visit date**, then the day of the **last visit date** will be assigned to the missing day.
- If either the year is before the year of the **last visit date** or if both years are the same but the month is before the month of the **last visit date**, then the last day of the month will be assigned to the missing day.

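### The SAP's treatment-emergent rule says *after* where the protocol says *at or after*; read strictly, it excludes AEs whose start date the SAP itself imputes to the first-dose date

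*SAP*

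**What the plan says.** **The two definitions.** Protocol 9.3.3.1: "A TEAE is defined as an AE that started or worsened at or after the start of study treatment". SAP 10.15.1 says that a TEAE "is defined as an AE that started or worsened after the start of study treatment". SAP 6.1 lists the changes from the protocol, and this one is not on the list, although the SAP is written against Protocol Amendment 1.

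**The reference point.** SAP 10.1: "Start of study treatment is defined as the date and time of first dose of either SOT101 or pembrolizumab, whichever occurs earliest". It is therefore a date and a time.

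**The AE onset.** Among the items to be determined for each AE, protocol 8.3.8.2 lists "Event duration, including onset date and end date". Neither document specifies an AE onset time.

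**The imputation.** SAP 10.16.1 has three rules that place an AE start on the first-dose date:
- Date completely missing: "the start date will be set to the date of the first dose of study medication".
- Day missing, in the month and year of first dose: "then the day of the first dose date will be assigned to the missing day".
- Day and month missing, in the year of first dose: "then the day and month of the first dose date will be assigned to the missing fields".

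The same section names TEAE derivation as a use of these imputed dates.

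**The concern.** The type, frequency and severity of TEAEs are a secondary endpoint. Assigning an unknown start to the first-dose date is normally the cautious choice, because it makes a doubtful event treatment-emergent. Under a rule that requires onset after the start of treatment, the same imputation has the opposite effect: the event lands on the boundary and the boundary is excluded.

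The first dosing day also matters clinically. Protocol 6.5.1 calls transient fever frequent after injection, and cycle 1 day 1 has the longest observation period in protocol 8.2.3. Pembrolizumab is given on day 1 of each cycle, and protocol 6.5.2.2 says that infusion reactions usually appear during or shortly after the infusion. Under Table 6.4 a grade 3 or 4 infusion reaction ends dosing, so such a reaction to the first infusion need not recur on a later day. If events dated on that day were left out, the TEAE tables would understate the safety profile.

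**Working it through.** No sample size, power or error rate depends on this, and the plan gives no figure to reproduce. The check is to apply SAP 10.16.1 and then compare dates under each definition.

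**Input (illustrative):** first dose on 15 March 2023. **Rules:** protocol, AE start ≥ first-dose date; SAP, AE start > first-dose date.

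| AE start as recorded | Date used | Protocol (≥) | SAP (>) |
|---|---|---|---|
| Complete, day before first dose | 14 Mar 2023 | no | no |
| Complete, first-dose day | 15 Mar 2023 | **yes** | **no** |
| Complete, day after | 16 Mar 2023 | yes | yes |
| Completely missing | 15 Mar 2023 | **yes** | **no** |
| Day missing, first-dose month | 15 Mar 2023 | **yes** | **no** |
| Day missing, earlier month | 28 Feb 2023 | no | no |
| Day missing, later month | 1 Apr 2023 | yes | yes |
| Day and month missing, first-dose year | 15 Mar 2023 | **yes** | **no** |
| Day and month missing, earlier year | 1 Jan 2022 | no | no |
| Day and month missing, later year | 1 Jan 2024 | yes | yes |

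Four of the ten cases change. Three of them are every imputation that lands on the first-dose date. The fourth is a complete date on the first-dose day.

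**Imputed dates.** These three cases do not depend on what the CRF collects, because SAP 10.16.1 imputes a date and no time. Take the case with only the day missing. With first dose on day 15 of a 31-day month, an AE that truly began on any of the 31 − 15 = 16 later days is moved to day 15 and is then not after it.

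**Complete dates.** Against a date and time, a reaction that follows the first injection is after it, and the two definitions differ only for an event at the exact moment of dosing. The event is lost only if the comparison is made on dates, which is what a programmer has if no onset time is recorded.

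**Restoring the words alone is not enough.** With a date-only onset and a date-time start, *at or after* also leaves the first-dose day undecided. If an imputed date were given a default time of midnight, it would precede the dose under either wording. A rule stated on dates is needed.

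**Size.** The documents do not give the number of AEs with missing start dates, or the share of patients whose only episode of a reaction falls on cycle 1 day 1. As an assumption, let that share be f and suppose the rule is programmed on dates. Take as the true rate the 81.0% for pyrexia under combination treatment in protocol 2.3, which comes from the earlier study. The tabulated rate is then 81.0% × (1 − f): 72.9% at f = 10%, 60.8% at f = 25% and 40.5% at f = 50%, with no loss at f = 0. This shows how the result depends on f; it is not an estimate for this trial.

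**The case against.** The strongest reply is that the SAP, read as a whole, means to count day-1 events. Section 10.1 fixes treatment start to a time, so a reaction to the first injection is literally after it. Section 10.6 begins the on-treatment period on the day of first dose, and section 10.5 puts that day on the post-start side when it numbers study days. The sentence before the definition in 10.15.1 treats non-emergent on-treatment events as exceptions, such as improvement of an existing condition. The imputation rule is cautious only if the first-dose date counts. On this view the missing words are a slip that a programmer would resolve correctly.

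Most of this stands. It makes the intention fairly clear, and it defeats the stronger inference a reader might draw, that all first-dose-day reactions drop out of the TEAE tables. That inference needs a rule the SAP does not state: an onset date strictly later than the first-dose date. It also needs the absence of an onset time. Protocol 8.3.8.2 only lists items to determine where possible; it is not the CRF, which was not available.

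The reply does not remove the conflict for imputed dates. There the stated rule and the stated imputation give a non-emergent result, and no tie rule says otherwise. That the intention can be inferred is a reason to write it down.

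The objection also limits the consequence. Repeat episodes are recorded separately (protocol 8.3.8.2) and dosing falls on four days of each cycle, so one later episode of the same term restores the patient to the table. Under SAP 12.8.1, AEs linked to an on-treatment AE count as emergent. The all-AE listing keeps non-emergent events, and most SAE and death summaries in SAP 12.8.1.2 are not worded as restricted to TEAEs.

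**Conclusion.** The point holds in a limited form. The SAP narrows a protocol safety definition without declaring it, and the narrowed rule contradicts the SAP's own imputation. Read strictly, AEs with a completely missing start date, and those with a partial date matching the first-dose month or year, are imputed to the first-dose date and then excluded from the TEAE tables. Imputations to an earlier or later month or year are unaffected.

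For AEs with a complete onset date on cycle 1 day 1 the conclusion is conditional. They are exposed only if the rule is programmed on dates, and the documents do not settle whether an onset time is collected.

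No magnitude can be claimed. The pyrexia figures under the check rest on an assumed share, on a rate from another study and on date-only programming. One-off day-1 reactions are the most exposed; recurring ones are largely protected. The primary endpoint is not touched.

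**What to change.** In SAP 10.15.1, restore *at or after* and add a tie rule on dates: an AE whose onset or worsening date, recorded or imputed under 10.16.1, is on or after the date of first dose is treatment-emergent, unless a recorded time shows that it began before dosing. The tie rule goes beyond the protocol's text, which does not mention dates, so it should be presented as a clarification. If the narrower definition was intended, list and justify it in SAP 6.1 and change the imputation to match.

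The cost is a sentence in the SAP and one comparison operator in the program. The downside is that a few complaints that began on day 1 before dosing may be counted as treatment-emergent where no time was recorded. That errs towards over-reporting, the conservative direction for safety.
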